## Waiver of Documentation of Consent

You indicated that a waiver of documentation of consent (verbal/oral consent) is requested.

1 \* Indicate why a waiver of documentation of consent is being requested for the study:

- The only record linking the subject and the research would be the consent document, and the principal risk would be potential harm resulting from a breach of confidentiality.
- The research presents no more than minimal risk of harm to subjects, and involves no procedures for which written consent is normally required outside of the research context.

2 \* Provide a justification/explanation for the choice above:

Waiver of documentation of consent is requested for probands and family members who choose not to have genetic testing. The study procedures include return of completed surveys and possible interview about attitudes and experience with genetic testing. These procedures represent no more than risk individuals encounter in everyday life. All of the essential elements of informed consent are included in the information / consent letter sent with the questionnaires. If a potential participant agrees to complete the survey, they will return the letter indicating their agreement.

ID: VIEW4E1C6EF6F5000  
Name: v2\_Waiver of Documentation of Consent

HP-00081981

Children (Assent)\_V2

## Children (Assent)

You indicated that children are included in this study.

1 \* From whom will assent be obtained?

- All children
- None of the children
- Some children

1.1 If assent will be obtained from some children, describe which children will not be asked for assent and why:

Written assent will be obtained from children 13-17 years of age. Younger children will have key points of the study explained in language understandable and appropriate to their developmental level and verbal assent will be obtained. For very young children and infants we will not obtain assent, but will not include any child who does not cooperate or seem unwilling to comply with the procedures.

2 \* How will assent be documented? (Answer "N/A" if assent will not be obtained from any of the children)

A signed IRB-approved assent form will document assent for minors age 13-17. For all children, an informed consent note will document the consent process, parental permission and manner in which assent was obtained.

ID: VIEW4E1B2E37C1C00  
Name: v2\_Children (Assent)

HP-00081981

Waiver of Assent\_V2

## Waiver of Assent

**1 \* Why is a waiver of child assent being requested?**

A waiver of assent is justified based upon the following:

- 1. The research involves no more than minimal risk to subjects
- 2. The waiver will not adversely affect the rights and welfare of the subjects
- 3. The research could not practicably be carried out without the waiver; and
- 4. Whenever appropriate, the subjects will be provided with additional pertinent information after participation.

**The capability of these children is so limited that they cannot reasonably be consulted (taking into account the ages, maturity, and psychological state of the children involved)**

- The intervention or procedure involved in the research holds out a prospect of direct benefit that is important to the health or well-being of the children and is available only in the context of the research

**2 \* Provide a justification/explanation for the choice above:**

A waiver of child assent is only being sought for those very young children who cannot reasonably be consulted.

ID: VIEW4E1B2E3AC3800  
Name: v2\_Waiver of Assent

HP-00081981

Consent Forms - Draft\_V2

## Consent and HIPAA Authorization Forms - Draft

1 Upload all of your Consent Forms for approval. Use only Microsoft Word.

Name	Created	Modified Date
 Family consent(0.03)	11/8/2018 2:31 PM	2/18/2020 4:11 PM
 Family assent(0.02)	11/8/2018 2:37 PM	2/18/2020 4:11 PM

**IMPORTANT NOTE:** the above list of consent forms (if any) are DRAFT versions. Under no circumstances should copies of these be distributed to patients/study subjects. If/when this research submission is approved by the IRB, approved consent forms will be available for download and use from the "Documents" tab of the Submission's workspace (click Exit and then look for the Documents tab - approved submissions only)

1A Archived Consent Forms:

Name	Created	Modified Date
------	---------	---------------

There are no items to display

2 Upload any HIPAA authorization forms here:

 HIPAA for Cascade study 10.31.18.doc(0.02)	11/8/2018 2:38 PM	12/17/2018 10:43 AM
--	-------------------	---------------------

Please refer to HRPO's website for specific instructions for preparing informed consent documents and to access current templates:  
<http://hrpo.umaryland.edu/researchers/consents.html>

ID: VIEW4E1C7712D3000  
Name: v2\_Consent Forms - Draft

## Organization Review Requirements (other than IRB)

Answer the following questions to determine additional organizational review requirements:

1 **Department/Division Review** - All research submissions are required to undergo department/division/institutional review prior to IRB review. The following entity is listed as the required department/division/institutional review:

*Med Endocrinology*

If this information is incorrect, please notify the HRPO office.

2 **RSC Review Criteria** - select 'Yes' if the answer is 'Yes' for any of the following questions. Review by the Radiation Safety Committee may be required.

\* 2.1 Does the research involve the use of ionizing radiation?

Yes  No

2.2 Does the research involve the sampling of radioactive human materials for subsequent use or analysis in a laboratory?

3 **IBC Review Criteria** - select 'Yes' if the answer is 'Yes' for any of the following questions. Review by the Institutional Biosafety Committee may be required.

\* 3.1 Does the research involve human gene transfer?

Yes  No

-OR-  
Does the research specifically apply to human studies in which induction or enhancement of an immune response to a vector-encoded microbial immunogen is the major goal, and such an immune response has been demonstrated in model systems, and the persistence of the vector-encoded immunogen is not expected? This type of research is often referred to as recombinant vaccine trials.

3.2 Does the research involve the exposure of human subjects to pathogenic microorganisms, or the exposure of research staff to human subjects or samples known or reasonably expected to carry infectious disease(s)?

3.3 Does the research involve the sampling of materials from persons with no known infectious disease and where the only risk to study staff is occupational exposure to bloodborne pathogens as defined by the OSHA Bloodborne Pathogen Standard?

4 **Cancer Center Criteria** - Answer the following to determine if review by the Cancer Center (Hematology-Oncology) may be required.

\* Does the protocol involve in any way studies related to the prevention, treatment, diagnosis, or imaging of neoplastic diseases?

Yes  No

5 **General Clinical Research Center Review Criteria** - the GCRC offers free and/or cost shared resources for patient-oriented research. [Click Here for more information.](#)

Answer the following to determine if review by the GCRC may be required.

\* Will the General Clinical Research Center (GCRC) facility or resources be used to conduct this activity?

Yes  No

6 **VA Review Criteria** - Answer the following questions to determine if review by the VAMHCS R&D Committee may be required.

\* 6.1 - Will the research be conducted by VA Investigators including PIs, Co-PIs, and Site Investigators on VA time (serving on compensated, WOC, or IPA appointments)?

Yes  No

\* 6.2 - Will the research utilize VA resources (e.g., equipment, funds, medical records, databases, tissues, etc.)?

Yes  No

\* 6.3 - Will the research be conducted on VA property, including space leased to and used by VA?

Yes  No

**PLEASE NOTE** that the research may be funded by VA, by other sponsors, or may be unfunded.

HP-00081981

Summary of Required Reviews\_V2

## Summary of Required Reviews (other than IRB)

1 **Additional Committee Reviews** - Based on your responses to the previous questions, you have identified the following additional reviews. To complete or view these additional committees' forms, click on the links below or exit this application and click on the appropriate button on left side of this submission's webpage.

Name of Related Submission

*This protocol has no related submissions (RSC, GCRC, IBC, etc)*

2 **Required Department and Specialty Reviews** - Based on the PI's organization (department, division, etc.) affiliation and answers to previous questions (use of Cancer Center, etc.), the organizations listed below are required to review this application. These reviews are conducted online and no additional forms or steps by the study team are required.

Name of Organization

Med Endocrinology  
Pediatrics

**Review Status**

Complete  
Complete

ID: VIEW4E1C8D9AE4000  
Name: v2\_Summary of Required Reviews (other than IRB)

HP-00081981

Additional Documents\_V2

## Additional Documents

1

Upload all additional documents here:

**Name****Created****Modified Date**

 ECG scheduling letter_070622.docx(0.01)	7/8/2022 2:46 PM	7/8/2022 2:46 PM
 COVID-19 Ed Activity Book-11-final (1) (1).pdf(0.01)	5/24/2021 10:46 AM	5/24/2021 10:46 AM
 arc newsletter 5.17.2021.pdf(0.01)	5/24/2021 10:25 AM	5/24/2021 10:25 AM
 COVID risk statement(0.01)	12/9/2020 1:58 PM	12/9/2020 1:58 PM
 LQTS COVID letter on letterhead_060820_clean.doc(0.03)	5/11/2020 4:39 PM	6/9/2020 11:22 AM
 Family member questionnaire only consent letter rev 010520.docx(0.02)	1/7/2019 1:20 PM	1/5/2020 2:07 PM

ID: VIEW4E0962513A000  
Name: v2\_additional Documents

HP-00081981

Final Page of Application\_V2

## Final Page of Application

**You have reached the final page of this application.** It is recommended that you click on the "Hide/Show Errors" link on the upper or lower breadcrumb row of this page. The "Hide/Show Errors" will do a search of your application, and highlight areas that are required or need to be completed prior to submitting.

By submitting this application, you are electronically routing the protocol for departmental scientific review and all other necessary reviews. According to information you have provided, this application will be routed to the following Departments for review prior to being forwarded to the IRB for review. These reviews are conducted online and no additional forms or steps by the study team are required.

Name of Organization	Review Status
Med Endocrinology	Complete
Pediatrics	Complete

**Required Safety Committee Reviews** - In addition to the IRB, the following committees must review this submission. Each additional committee has a separate online form that the study team will be required to fill out. All committee applications (IRB plus those listed here) must be completed properly before the 'package' of applications can be submitted. The team may complete these additional forms in any order or at any time prior to submission of the IRB Application. To complete or view these additional committees' forms, click on the links below or exit this application and click on the appropriate button on left side of this submission's Workspace.

Name of Related Submission

*This protocol has no related submissions (RSC, GCRC, IBC, etc)*

You may check the progress of your application at any time by returning to the Workspace of this submission. A detailed history, including notes, dates, and times of events, is provided to you for this purpose.

If a reviewer returns the application to you, you must address their concerns and resubmit the protocol for review to all designated departments. After all departments have reviewed the application, it will automatically be sent to the IRB for review. Changes made to the submission after its approval must be submitted as modifications.

**Click the "Finish" button and then click "Submit Application" in the submission Workspace.**

ID: VIEW4E1B10C500000  
Name: v2\_Final Page of Application

## **STATISTICAL DESIGN AND STUDY POWER**

### **A. Power Calculations**

#### **A1. Aim 1 (cascade screening intervention)**

Our study is based on 70 *KCNQ1* Thr224Met probands who were identified as part of another research study and chose to undergo clinical confirmation of their genotype and clinical evaluation for long QT syndrome. We cannot approach probands who chose not to undergo the return of results process. These 70 probands have over 700 first degree family members who may be eligible for cascade screening with our intervention. We can assume some of the family members have died and some may not live in Lancaster County, but a very large proportion will be eligible for testing. Due to privacy laws we cannot approach a family member directly who has not first been contacted by the proband. We will provide family letters to probands for them to share with family members, but this is a personal decision for each proband. This study will compare the rate of uptake of cascade screening before and after our intervention of a simplified cascade screening program. Given that an individual who undergoes cascade screening before our intervention, during the 'traditional' period does not need to undergo testing again, we cannot statistically compare the difference in the proportion of family members who undergo cascade screening before and after the intervention or the statistical power that our study will have to detect a difference in uptake. That being said, our experience suggests that uptake of cascade screening will be very low among the Amish during the 'traditional' phase when cost, transportation, and an invasive test are barriers. This pilot study will test whether we can overcome these barriers and detect a *meaningful* improvement in uptake of cascade screening, disclosure to family members, and uptake of appropriate medical intervention. We will define this meaningful improvement *a priori* as a 15% improvement. For example, If we have 3% of eligible individuals undergo cascade screening during the traditional phase, we would deem 18% of eligible individuals getting tested a clinically meaningful increase. This would translate into 15/500 getting tested before our intervention and 87/485 getting tested after implementing our intervention. Another way of looking at this is that approximately 2-3 probands would initiate cascade screening before the intervention and 12-13 would after the intervention (assuming 7 children per proband).

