## Study Procedures

**If you uploaded a separate research protocol document in the 'Research Protocol' page, cite the applicable section and page numbers from that document in the answer boxes below. (If this study is a collaborative UM/VA study please list each procedure that is being conducted and the locations where it is being conducted.)**

1 \* Describe all procedures being performed for research purposes only (these procedures would not be done if individuals were not in the study) and when they are performed, including procedures being performed to monitor subjects for safety or to minimize risks:

Individuals who participated in the KCNQ1 ROR study (probands) and their first degree blood-related family members will be invited to participate. All probands will be mailed an information / consent letter with a response form (uploaded in Informed Consent Section), a questionnaire about their attitudes and experience with genetic testing (uploaded to Surveys Section), and a sample family invitation letter (uploaded to Recruitment Section). In the consent letter, probands will be asked to complete and return the questionnaire as an indication that they agree to join the study. They will be informed that they may be asked to participate in an in-person interview. The letter will also ask if we can invite their adult first-degree family members who live locally to take part in the study, whether or not the proband participates. They will be given the option to enroll their minor children (with appropriate consent and assent) in the free cascade testing portion of the study. The proband will complete and return the response card to indicate whether they agree to contact of family members.

With the proband's permission, the family invitation letter will be mailed to the first-degree family members of the proband who live locally, using information from the 2009 Fisher Book and 2018 Address book of the Lancaster County Amish. At the proband's request, copies of the family invitation letter will, instead, be mailed to the proband so they can hand deliver them to family members of their choosing.

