**1 \* Provide the rationale and sample size calculations for the proposed target population:**

Our study is based on 88 KCNQ1 Thr224Met probands who were identified as part of another research study and chose to undergo clinical confirmation of their genotype and clinical evaluation for long QT syndrome. We cannot approach probands who chose not to undergo the return of results process. These 88 probands have over 700 first degree family members who may be eligible for cascade screening with our intervention. We can assume some of the family members have died and some may not live in Lancaster County, but a very large proportion will be eligible for testing. Due to privacy laws we cannot approach a family member without permission from the proband. With permission from the proband, we will send family letters or we will provide family letters to probands for them to share with family members. This study will compare the rate of uptake of cascade screening before and after our intervention of a simplified cascade screening program. Given that an individual who undergoes cascade screening before our intervention, during the 'traditional' period does not need to undergo testing again, we cannot statistically compare the difference in the proportion of family members who undergo cascade screening before and after the intervention or the statistical power that our study will have to detect a difference in uptake. That being said, our experience suggests that uptake of cascade screening will be very low among the Amish during the 'traditional' phase when cost, transportation, and an invasive test are barriers. This pilot study will test whether we can overcome these barriers and detect a meaningful improvement in uptake of cascade screening, disclosure to family members, and uptake of appropriate medical intervention. We will define this meaningful improvement a priori as a 15% improvement. For example, if we have 3% of eligible individuals undergo cascade screening during the traditional phase, we would deem 18% of eligible individuals getting tested a clinically meaningful increase. This would translate into 15/500 getting tested before our intervention and 87/485 getting tested after implementing our intervention. Another way of looking at this is that approximately 2-3 probands would initiate cascade screening before the intervention and 12-13 would after the intervention (assuming 7 children per proband).

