### **B1.2 Secondary outcomes**

- a. Extent of disclosure of genotype results before and after the intervention. This outcome is defined as the number of family members (siblings and children) told (reported via survey) out of the total number of proband first degree relatives (known from the Fisher Book and asked on the survey).
- b. Proportion of informed first-degree relatives who get screened before and after the intervention. This outcome is defined as the number of family members tested out of the number told by probands (reported via surveys)
- c. The overall rate of uptake of preventative therapy among probands and family members (e.g., see a cardiologist and/or take a beta-blockers)

Analyses of secondary outcomes (a) and (b) will occur in the same manner as the primary outcome, by comparing proportions before and after the intervention. For secondary outcome (c), we don't expect the proportion of appropriately treated carriers to be impacted by our intervention, but rather the absolute number of treated individuals would be impacted by detecting more carriers with improved cascade screening. For the disclosure outcome (a), we will compare results using the denominator based on Fisher book data and based on data reported in the survey. For the uptake of screening among those informed outcome (b), the denominator is based on the survey results (the proband will be asked who they disclosed results to and the family member will be asked if their family member told them). For the uptake of clinical recommendation outcome (c), we will use data from the participants' charts to determine whether beta-blocker therapy was indicated and prescribed. We will gather data from the survey on whether participants are following the recommendations. While we don't expect our intervention to change the proportion of individuals appropriately treated, we will compare the proportions before and after the intervention to confirm this assumption.

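### Secondary outcome (b) divides all relatives tested by those told by the proband, but the protocol, unlike the SAP, lets the study inform relatives by post, which inflates (b) in the simplified period only

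*Combined protocol and SAP*

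**What the plan says.** **Contact route in the SAP** (section A1). The rule is "we cannot approach a family member directly who has not first been contacted by the proband". The letters reach relatives through the proband: "We will provide family letters to probands for them to share with family members".

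**Contact route in the protocol.** Under Sample Size and Data Analysis, item 1, the condition is permission, not prior contact: "Due to privacy laws we cannot approach a family member without permission from the proband". It continues: "With permission from the proband, we will send family letters or we will provide family letters to probands". Study Procedures makes study mailing the default once permission is given: "the family invitation letter will be mailed to the first-degree family members of the proband who live locally". Hand delivery is the alternative: "At the proband's request, copies of the family invitation letter will, instead, be mailed to the proband". The Recruitment section repeats this arrangement. The Informed Consent Process section adds that relatives may be visited at home after returning a response card, or possibly with no response at all.

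**Outcome definitions** (SAP B1.2, with the same definitions in the protocol's data analysis plan). Outcome (a), extent of disclosure, is "the number of family members (siblings and children) told (reported via survey) out of the total number of proband first degree relatives". Outcome (b) is titled as a proportion of informed relatives, but it is computed as relatives tested over relatives told by probands, as reported on surveys. SAP B1.1 takes the number screened, for all outcomes, from charts. As described, the surveys ask probands to whom they disclosed, and ask relatives whether their family member told them. Neither document says how to classify a relative who learned of the testing only from the study's letter or a visit.

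**The concern.** The two documents describe different routes by which a relative comes to know about testing, and the definition of (b) suits only the SAP's route. If the proband always makes the first contact, the number told by probands is a fair stand-in for the number informed. If the study writes to relatives on the strength of a permission card, it is not.

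The mismatch is one-sided in time. Study letters and visits belong to the intervention. In the traditional period relatives depended on the counselling advice given to probands. A relative who is tested after a study letter alone therefore enters the numerator of (b) only in the simplified period, and never enters its denominator. The before/after comparison of (b) is meant to show whether informed relatives become more likely to be tested. As defined, it can rise when nobody's readiness to be tested has changed.

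**Working it through.** **The plan's example first** (SAP A1 and protocol Sample Size, item 1). Before: 15/500 = 3.0%. Remaining eligible: 500 − 15 = 485. After: 0.18 × 485 = 87.3, given as 87, and 87/485 = 17.9%. The figures reproduce.

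**Structure of (b).** In the simplified period let
- *t* = share of relatives told by the proband,
- *m* = share reached only by the study (letter or visit),
- *q* = probability of testing among those told,
- *r* = probability of testing among those reached only by the study.

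Relatives tested are proportional to *qt + rm*, and the denominator of (b) is proportional to *t*. So

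(b) as defined = (*qt + rm*)/*t* = *q* + *r·m/t*.

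The quantity that the title describes is (*qt + rm*)/(*t + m*). The surplus *r·m/t* is zero only if nobody is reached by the study alone or none of those people is tested. In the traditional period there is no study letter, so *m* = 0 and this surplus is absent.

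**Illustrations.** The documents give none of *t*, *m*, *q* or *r*, so the values below are assumptions.

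1. Fixed behaviour, *q* = *r* = 30%:

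| Told (*t*) | *m* = 0 | *m* = 20% | *m* = 40% |
|---|---|---|---|
| 20% | 30% | 0.30 + 0.30 × 0.20/0.20 = 60% | 0.30 + 0.30 × 0.40/0.20 = 90% |
| 10% | 30% | 0.30 + 0.30 × 0.20/0.10 = 90% | 0.30 + 0.30 × 0.40/0.10 = 150% |

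   Over all informed relatives the value is 30% in every cell.

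2. Relatives reached only by the study test half as often, *r* = 15%, with *q* = 30% and *t* = 20%. With *m* = 20%, (b) = 0.30 + 0.15 × 0.20/0.20 = 45%. With *m* = 40%, it is 0.30 + 0.15 × 0.40/0.20 = 60%. The true proportion among the informed falls, to (0.06 + 0.03)/0.40 = 22.5% and (0.06 + 0.06)/0.60 = 20%.

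3. The plan's 87 tests among 485, with 30% told (145.5): (b) as defined is 87/145.5 = 60% whatever the mailed share. Over everyone informed it is 60%, 87/242.5 = 36% or 87/339.5 = 26% for *m* = 0, 20% or 40%.

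**When (b) stops being a proportion.** With 87 tested, (b) exceeds 100% once fewer than 87 relatives are reported as told, which is 87/485 = 17.9%. At 10% told it is 87/48.5 = 179%.

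**The case against.** The best case against runs as follows.

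- *The gap is not created by the mailing.* The SAP speaks of the proband contacting a relative, which is not the same as disclosing a result. A relative could also hear from a tested sibling under either route. This stands: direct mailing widens an existing gap. But it does so in one period only, and that is what distorts a before/after contrast.
- *Other causes could push (b) above 100%.* SAP B1.3 expects about 60% of surveys back, and a chart numerator over an incomplete survey denominator can do the same without any mailing. This also stands. The threshold above shows that the definition is unsafe. It does not measure the effect of mailing alone.
- *The shares are unknown.* Correct. Probands may also ask for hand delivery, so the mailed-only share could be small.
- *These are secondary outcomes in a pilot.* True, and it limits the weight of the point. The plan still compares (b) before and after.

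A reader might go further and infer that outcome (a) is misread. The documents do not support that. Outcome (a) is meant to measure whether probands tell more relatives, and the survey asks probands whom they told. If mailing replaces telling and (a) falls, that is a true result about proband disclosure. It would be distorted only if respondents counted a study letter as telling. The questionnaires and the family letter are not shown, so this cannot be judged. Relatives' own answers offer a second source.

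A reader might also infer that the primary outcome is affected. Its denominator is all eligible relatives in the Fisher book and does not depend on who delivers the letter. Splitting uptake by delivery route would not help, because probands choose the route and the comparison would be confounded.

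**Conclusion.** The SAP and the protocol contradict each other on how relatives are contacted. Under the protocol's route, (b) as defined is wrong for the simplified period: it counts every relative tested but divides by only those told by probands. The bias favours the intervention and is absent from the traditional period. It requires only that some relatives reached by the study alone are tested.

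Its size cannot be stated from the documents. Under the assumed shares above, with behaviour held fixed at 30% and 20% told, (b) reads 60% or 90%. With the plan's 87 tests it passes 100% when fewer than 87 relatives are reported as told. Outcome (a) remains a valid measure of proband disclosure, provided that a study letter is not counted as telling.

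**What to change.** 1. Rewrite the contact rule in SAP A1 to match the protocol's Study Procedures, Sample Size and Recruitment sections, and acknowledge the home visits described under Informed Consent Process.
2. For each relative, record how they were informed (proband, study letter, home visit, more than one, none) from study contact records and the surveys. Study records alone will not show who received a hand-delivered letter, so the survey answers are needed too.
3. State that (a) counts only telling by the proband, in both periods, and report reach by study letter separately.
4. Define (b) as relatives tested among those informed by any route, with the numerator restricted to relatives in the denominator. Report the told-by-proband version as a separate analysis, with its numerator restricted in the same way.

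The cost is SAP wording, a contact record and one classification per relative, with no added participants or visits. The downsides are that (b) may look less favourable, and that the route will be missing for some relatives where surveys are not returned. The number unclassified should be reported in each period.
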